9. DATA MANAGEMENT AND STATISTICAL CONSIDERATIONS

9.1. Data management

CIC-CPCET Pharmacometry unit will be responsible for activities associated with the data management of this study. This will include setting up a relevant database and data transfer mechanisms, along with appropriate validation of data and resolution of queries. Data generated within this clinical study will be handled according to the relevant SOPs of the data management and biostatistics unit.

A detailed Data Management Plan (DMP) will be established before the study initiation.

9.1.1. Data collection

All the results will be recorded in an electronic CRF for each subject. Designated study site staff will enter data required by the protocol into CRFs.

All data obtained in this study should be source-documented. The appropriate study site staff will record all data on source documents immediately. If any form of printout is available, each copy of such printouts should be dated, signed by the investigator and attached to the subject's file.

It is the responsibility of the investigator to ensure that CRFs are kept up to date so that they always contain the latest observations on the subjects enrolled. Corrections to CRFs will be made directly into the CRF by the investigator or an authorised staff member. For any correction made, user's identification, date and reason(s) for the change will be reported in the audit trail.

All supportive documentation in addition to the CRF, such as laboratory results, ECG traces must be clearly identified with the study code, the subject's number and initials. Any personal information, including the subject's name, must be removed or rendered illegible to preserve individual confidentiality.

9.1.2. External Data

External data will concern PK data (Excel files provided by laboratory and by PK modeling). A data transfer protocol will be validated, and the data will be directly imported into the study database.

9.1.3. Data validation

Consistency checks will be implemented according to the DMP. If inconsistencies are detected, queries will be generated using eCRF queries and all queries will be documented in an audit file.

9.1.4. *Data coding*

Adverse events (AEs) and medical histories will be coded according to the Medical Dictionary for Regulatory Activities (MedDRA 21.0 or the latest available version at the study completion date). Concomitant medications will be coded according to the ATC codes.

9.1.5. *Data Review meeting*

A Data Review meeting will be organized before locking the database at the end of each study part (*i.e.* end of SAD and end of MAD). Reconciliation of pharmacovigilance database and study database will be done before each meeting.

The study database will be locked in SAS export format. Formatted database will be transferred for statistical analysis.

A data management report will document all steps at the end of the study.

9.2. **Sample Size Considerations**

No formal sample size calculation has been performed (no formal hypothesis will be tested). The sample size is based on empirical considerations and on the literature.

Nevertheless, a sample size of 6 subjects receiving an active drug provides a chance of 26% to observe at least one adverse event, with a true adverse event rate estimated to 5%. This level of predictability is deemed adequate for this FTIH study.

No sample size re-estimation will be planned.

9.3. **Data Analysis Considerations**

Statistical analysis will be performed by the Pharmacometrics unit of the Clinical Pharmacology department.

Complete details of the planned statistical analyses will be provided in the Statistical Analysis Plan (SAP).

Patients' characteristics and safety data will be analyzed using SAS® software version 9.4 (SAS Institute Inc., Cary, NC, USA).

Pharmacokinetic data will be analyzed using NONMEM ICON Development Solutions v7.4) and R software (www.r-project.org, v3.2.2).

9.3.1. *Description of data sets*

Several populations will be considered:

The Included set will be defined as all included subjects.

The Randomized set will be defined as all randomized subjects.

The Safety set will be defined as all included subjects having taken at least one dose of IMP.

The PK set will be defined as all randomized subjects having taken at least one dose of IMP without protocol deviation affecting PK evaluation and with available PK data.

The analysis sets will be validated during the final data review meeting.

A summary of protocol deviations by treatment group and the corresponding listing by subject will be generated.

9.3.2. *Hypothesis and statistics*

No formal statistical hypothesis will be tested. Safety data including but not limited to AEs, vital signs, ECGs, and laboratory safety tests will be descriptively summarized by doses.

Estimation approach will be adopted to estimate both the between- and within-subject PK variability and to assess the dose proportionality following single dosing of IFB-088.

Descriptive statistics will be supplied according to the nature of the criteria:

- Quantitative variables: sample size, arithmetic mean, standard deviation (SD), median, minimum and maximum (with geometric mean and coefficient of variation (CV) for PK);
- Qualitative variables: sample size, absolute and relative frequencies per class.

9.3.3. *Interim Analysis and/or schedule of analyses*

No formal interim analysis is planned. During dose escalation phases, PK and safety data will be reviewed on an in-stream basis to inform the dose escalation decision.

Statistical analyses will be performed after achievement of each cohort in order to provide ongoing safety, PK data so that the DEC can have access to all information they need to decide the dose escalation. A statistical report will be generated for each DEC meeting, the content will be detailed in the DEC charter.

A final analysis will be done after SAD part and after MAD part, statistical results will be presented in the clinical study report.

9.3.4. *Handling of dropouts and missing data*

Dropout subjects will not be analyzed for pharmacokinetics.

No repositioning of visits will be done.

If not otherwise stated:

- Missing data other than baseline values will not be replaced.
- Baseline for safety parameters will be defined as the last available parameter value before and closest to the first dosing.

9.3.5. *Demographic and baseline characteristics*

The following analysis will be performed on the Randomized set.

The subjects' demographic and baseline characteristics will be summarized by treatment group and listed by subject.

Tables by treatment group with the number of subjects having at least one medical or surgical history and the corresponding listing by subject will be edited; by system organ class and preferred term, if relevant (MedDRA). Tables by treatment group with the number of subjects having at least one previous treatment and concomitant treatment and the corresponding listing by subject will be prepared.

Baseline safety parameters:

Individual safety data (clinical laboratory, vital signs, ECG and physical examination) measured before the first drug administration will be checked for validity of entrance criteria, and abnormalities will be documented. Abnormal physical findings at baseline will be listed. Individual abnormalities before dosing will be flagged in data listings and presented along with post-dose measurements in the statistical appendices.

9.3.6. *Study drug and concomitant therapy*

Drug dispensing information and details of drug dosing (actual treatment received, actual dose received, date and time of drug intake) for each subject will be listed by treatment group.

Subjects who received concomitant treatments along with the study drug will be listed by treatment group and subject. If relevant, concomitant medications will also be summarized by anatomic class and therapeutic class (ATC drug dictionary) for each treatment group and overall subjects, presenting the frequency of subjects (n) taking a given medication and the number of occurrence of each medication.

9.3.7. *Safety Analyses*

Safety data will be presented in tabular and/or graphical format and summarized descriptively according to standard international guidelines.

9.3.7.1. *Criteria*

- Adverse events
- Vital signs: supine and standing systolic and diastolic blood pressure, pulse rate, tympanic temperature
- Standard 12-lead ECG
- Laboratory parameters: hematology, coagulation, biochemistry, urinalysis
- Physical examination
- Vigilance (Bond and Lader VAS)

9.3.7.2. *Methodology*

Laboratory data (hematology, biochemistry, coagulation and urinalysis), vital signs, vigilance VAS and ECG parameters, (raw data and changes from baseline) will be described.

In addition, vital signs, ECG and laboratory data could be compared to potentially clinically significant range (PCSA) to be specified in the SAP.

All these parameters will be listed by subject and assessment time. Data that is out of normal ranges will be flagged as well clinical significance.

Adverse events (AEs) will be coded according to the Medical Dictionary for Regulatory Activities (MedDRA version 21.0). They will be classified into pre-defined standard categories according to chronological criteria:

- Pre-treatment AEs are defined as AEs that occurred or worsened (or become serious) prior to the first study drug administration.
- The treatment-emergent AEs (TEAEs) are defined as AEs that occurred or worsened (or become serious) during an exposure of study drug.

The number of subjects with at least one adverse event and number of AEs for each treatment group will be summarized by categories, and if relevant detailed by system organ class and preferred term.

All safety analyses will be based on the TEAEs using the safety set. Pre-treatment AEs will be listed by subject in statistical appendices.

TEAEs will be summarized by treatment group:

- The number and percentage of subjects with at least one TEAE overall, any severe TEAE, any serious TEAE, and any TEAE leading to treatment discontinuation.
- The number and percentage of subjects with at least one TEAE by system-organ class and preferred term.
- The number of occurrences of TEAE by system-organ class and preferred term.

Subjects presenting TEAEs will be listed, sorted by, treatment, system organ class, and preferred term.

Serious adverse events will be listed, sorted by treatment and subject.

9.3.8. *Pharmacokinetic Analyses*

A non-compartmental analysis to calculate pharmacokinetic parameters of IFB-088 and IFB-139 in plasma and urine (described in [§3.2.2](#)) will be performed by the Pharmacometrics Unit.

Plasma concentrations of IFB-088 will be used to estimate pharmacokinetics parameters in human and compare to estimated pharmacokinetics parameters from inter-species model. Pharmacokinetic modeling will be performed using a non-linear mixed effects model with

NONMEM software (ICON Development Solutions v7.4). Data will be analysed using a first order conditional estimation method. The R software (www.r-project.org, v3.2.2) will be used for goodness-of-fit diagnostics and graphical displays.

Pharmacokinetics data of SAD will be analyzed using a population pharmacokinetic modeling approach to develop a pharmacokinetic model in human. This new pharmacokinetic model will be used to estimate pharmacokinetic parameters and variability in human and simulate new dosing schemes (with AUC and Cmax information) to help choosing the doses for MAD.

Pharmacokinetic modeling will be performed by the Pharmacometrics Unit.

Pharmacokinetic data will be listed and presented in graphical and/or tabular form as appropriate to the data, and will be summarized descriptively.

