4. STUDY POPULATION

4.1. Number of Subjects

A sufficient number of subjects will be enrolled so that 8 subjects will complete dosing and critical assessments for each of the cohorts. Six cohorts are planned in the SAD part (48 subjects) and 3 cohorts in the MAD part (24 subjects).

If a subject is withdrawn from the study, the subject may be replaced as necessary with another subject assigned to the same treatment with respect to active and placebo doses at the discretion of the sponsor's team in consultation with the investigator.

Subjects will be recruited from the clinical unit's database and via advertisements through mailing lists or announcement. The advertisement will be submitted to the Ethics Committee.

Inclusion of the same subjects in the 2 successive parts of the study (SAD then MAD) is possible, provided that the subjects have not met any discontinuation criteria during the first part, that they are not in the exclusion period (i.e. one month for SAD) and that they do not exceed the earnings for the last 12 months (*EMA Guidelines on strategies to identify and mitigate risks for first-in-human and early clinical trials with investigational medicinal products Paragraph 8.2.5*).

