6.5.3.3. *Follow-up / End of study visit (7 to 14 days post dose)*

The following procedures will be performed

- Vital signs measurement (including tympanic body temperature),
- Physical examination update,
- 12-lead ECG,
- Laboratory evaluation (hematology, coagulation, biochemistry and urinalysis),
- AE monitoring,
- Review of concomitant medications.

6.5.4. *MAD*

See Flow-Chart Section [3.5.3](#)

6.5.4.1. *Dosing Day (D1)*

The first administration of the study drug will be done after an overnight fast of at least 8 hours.

Subjects will have the following procedures performed at pre-dose:

- Verification of the eligibility criteria,
- Vital signs in triplicate except tympanic temperature,
- 12-lead ECG in triplicate,
- PK blood sampling,
- PK urine sampling (baseline),
- AE monitoring,
- Vigilance assessment.

The daily dose planned in each cohort will be administered in 2 intakes separated by a 12-hour interval, the first intake in the morning at 8:00 am and the second one at 8:00 pm in the evening.

The intake hour (H0) on Day 1 morning will be the reference time for implementing the following procedures at several time-points (see Flow chart Section [3.5.3](#)):

- Vital signs (including tympanic body temperature),
- 12-lead ECG,
- Diuresis monitoring,
- PK blood sampling at several time points,
- PK urine sampling,
- AE monitoring,
- Vigilance assessment at pre-dose, 1.5h post first dose and 12h post first dose before evening dose.

All assessments planned at 12h post first dose will be performed before the evening dose.

6.5.4.2. *Day 2*

The following procedures will be performed at several time points:

- Study treatment dosing in 2 daily administrations separated by an interval of 12 hours,

- Vital signs (including tympanic body temperature) before morning dose,
- Diuresis monitoring,
- PK blood sampling (17h, 19h, 21h and 24h post first dose of Day 1, just before the Day 2 morning dose),
- PK urine sampling (end of collection interval T12-T24h of Day 1),
- AE monitoring.

6.5.4.3. *Day 3 to Day 13*

The following procedures will be performed at several time points:

- Study treatment dosing in 2 daily administrations separated by an interval of 12 hours,
- Vital signs every morning before dosing,
- Tympanic body temperature in the morning before dosing on Day 4, Day 6, Day 8, Day 10 and Day 12,
- 12-lead ECG on Day 3, Day 6, Day 10 and Day 13,
- Diuresis monitoring on Day 6,

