- Safety laboratory tests (hematology, coagulation, biochemistry) in fasting state, at Day 3, Day 6, Day 10 and Day 13,
- Urinalysis on Day 3, Day 6, Day 10 and Day 13,
- PK blood sampling in the morning at Day 7 pre-dose, then 1h and 2h post morning dose,
- PK urine sampling on Day 6: pre dose, 0-4h and 4-12h,
- AE monitoring.

6.5.4.4. *Day 14*

The following procedures will be performed at several time points (see Flow chart Section [3.5.3](#)):

- Study treatment dosing in 2 daily administrations separated by an interval of 12 hours,
- Vital signs (including tympanic body temperature) in the morning pre-dose,
- Diuresis monitoring,
- PK blood sampling,
- PK urine sampling,
- AE monitoring,

- Vigilance assessment at pre-dose, 1.5h post first dose and 12h post morning dose.

6.5.4.5. *Day 15 to Day 17*

The following procedures will be performed:

- Full physical exam at Day 17 before discharge,
- Vital signs every morning,
- Tympanic body temperature at Day 17,
- Safety laboratory tests (hematology, coagulation, biochemistry) in fasting state at Day 17,
- Urinalysis on Day 17,
- 12-lead ECG on Day 17,
- Diuresis monitoring on Day 15 and Day 16,
- PK blood sampling on Day 15 (17h, 19h, 21h, 24h, 30h, 36h and 42h post Day 14 morning dose) and on Day 16 (48h and 60h post Day 14 morning dose),
- PK urine sampling on Day 15 (end of collection of T12-24h and T24-36h post Day 14 morning dose) and on Day 16 (T36-48h post Day 14 morning dose),
- AE monitoring,
- Discharge after assessment of scheduled evaluations and medical authorization.

The subject will be asked to return for a follow-up visit, scheduled 7 to 14 days post last dose.

6.5.4.6. *Follow-up / End of study visit (7 to 14 days post last dose)*

The following procedures will be performed

- Vital signs measurement (including tympanic body temperature)
- Full physical examination,
- 12-lead ECG,
- Laboratory evaluation (hematology, coagulation, biochemistry and urinalysis),
- AE monitoring,
- Review of concomitant medications.

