7. COMPLETION OR EARLY WITHDRAWAL OF SUBJECTS

7.1. Subject Completion

A completed subject is one who has completed all phases of the study including the follow-up visit.

The end of the study is defined as the last subject's last visit.

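### Section 9.3.4 bars undefined dropouts from all PK analysis, contradicts the PK set in Section 9.3.1, and would leave valid MAD data unused

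*Combined protocol and SAP*

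**What the plan says.** Section 9.3.4 (Handling of dropouts and missing data) opens with the rule "Dropout subjects will not be analyzed for pharmacokinetics". It sets no limit by study part, day, parameter or reason for leaving.

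Section 9.3.1 defines the analysis population differently: "The PK set will be defined as all randomized subjects having taken at least one dose of IMP without protocol deviation affecting PK evaluation", with the further condition that PK data are available. Completion is not required. On timing it adds: "The analysis sets will be validated during the final data review meeting". Section 9.3 defers full analysis details to a SAP, and no separate SAP text is part of the document.

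*Dropout* is not defined anywhere. The nearest text is Section 7.1, "A completed subject is one who has completed all phases of the study including the follow-up visit", and Section 4.1, which uses a different standard: "A sufficient number of subjects will be enrolled so that 8 subjects will complete dosing and critical assessments for each of the cohorts".

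**The concern.** The two sections give different answers for the same subject. Someone withdrawn partway through MAD, with a clean Day 1 profile, belongs to the PK set under Section 9.3.1 and is barred from PK analysis under Section 9.3.4. If the 9.3.4 sentence is meant only for subjects without usable PK data, it is redundant, because 9.3.1 already requires available data. If it is meant more widely, it removes valid data.

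PK is the secondary objective and rests on six active subjects per dose. Section 9.3.2 also plans to estimate between- and within-subject PK variability, which is hard enough at that size. The only planned points of decision are a data review meeting held once the data are in and a SAP not supplied here, and the document gives neither a rule to apply. The effect falls mainly on MAD, because Section 1.2.3 already reports SAD PK results.

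**Working it through.** **1. Sample counts, checked against the plan's own total.** Section 6.7.2 lists MAD plasma PK samples by day: D1 12, D2 4, D7 3, D14 12, D15 7, D16 2.

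- Sum: 12 + 4 + 3 + 12 + 7 + 2 = 40 samples, at 8 mL each = 320 mL.
- Safety blood: 18.7 mL at screening plus seven draws of 10.2 mL = 90.1 mL.
- Total: 320 + 90.1 = 410.1 mL, the figure stated in Section 6.7.2. The synopsis time points also give 40 (15 + 1 + 3 + 15 + 4 + 2).

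**2. What exists before a laboratory-driven withdrawal.** Under Section 6.5.4.2 the Day 1 profile ends with the 24 h sample, taken before the Day 2 morning dose. It has 12 + 4 = 16 samples. Section 6.5.4.3 then schedules "Safety laboratory tests (hematology, coagulation, biochemistry) in fasting state, at Day 3, Day 6, Day 10 and Day 13", so every on-treatment laboratory day follows a complete Day 1 profile.

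| Subject leaves | Plasma samples already drawn | Used under 9.3.1 | Used under 9.3.4, read literally |
|---|---|---|---|
| D3 or D6 laboratory day | 16 of 40 (40%) | 16 | 0 |
| D8 to D13 (includes D10, D13) | 16 + 3 = 19 of 40 (47.5%) | 19 | 0 |

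Urine PK collections in the synopsis number 4 (D1) + 3 (D6) + 4 (D14) + 1 (D15) + 1 (D16) = 13. By D8, 4 + 3 = 7 of 13 have been made, and these are lost as well.

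**3. Precision.** For a log-normal parameter, the half-width of the 95% CI of the geometric mean on the log scale is t(0.975, n−1) × σ / √n. The multiplier of σ is 0.925 for n = 7, 1.049 for n = 6 and 1.242 for n = 5.

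- No replacement, five instead of six: 1.242 / 1.049 = 1.18, so 18% wider at any CV.
- Replaced, six instead of seven: 1.049 / 0.925 = 1.13, so 13% wider.

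As a multiplicative factor, exp(half-width) with σ = √ln(1 + CV²):

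| CV | σ | n = 7 | n = 6 | n = 5 |
|---|---|---|---|---|
| 20% (assumed) | 0.198 | 1.20 | 1.23 | 1.28 |
| 39.8% | 0.383 | 1.43 | 1.50 | 1.61 |
| 60% (assumed) | 0.555 | 1.67 | 1.79 | 1.99 |

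The middle row takes the SAD AUC0-24h of 51.41 ± 20.45 ng/ml.h in Section 1.2.3.2 and assumes that 20.45 is a standard deviation: 20.45 / 51.41 = 39.8%.

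**4. How likely the case is.** The document gives no dropout rate. For assumed rates of 2%, 5%, 10% and 15% per subject, the chance of at least one dropout among the 18 active MAD subjects, 1 − (1 − rate)^18, is 30%, 60%, 85% and 95%.

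**The case against.** The strongest reply is that this is loose drafting and not a contradiction: a specific handling rule may narrow a general set definition, and the SAP or the data review meeting could settle it. That is possible. But no supplied text does so, and choosing after the data are in, with no stated rule, is a weak position.

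Several narrower points stand and limit the size of the loss:

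- The rule says dropouts are not analyzed. Section 9.3.8 has PK data listed, so the values may still appear in listings. The loss is from the summaries and the model.
- Section 9.3.2 plans no confidence interval for PK. The widths above measure precision; they are not a planned output.
- Only active subjects matter, since placebo samples carry no drug information.
- Among the laboratory criteria, the renal ones (3.4.3.3) withdraw the subject from the study. The liver and triglyceride rules (3.4.3.1, 3.4.3.2) stop treatment. Whether a subject off treatment but still followed is a dropout is unclear, which is part of the problem.
- A subject who leaves on Day 1, for QTc for example, has a truncated profile, and excluding him costs less.
- Replacement may restore six active subjects (4.1, 7.3). It is discretionary and does not recover the withdrawn subject's data.

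The document also wants PK from some withdrawn subjects: Section 8.10 asks for a PK blood sample from those with ALT at or above 3×ULN, who are taken off treatment. That sample may serve individual safety review only, but it fits poorly with a blanket bar.

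**Conclusion.** The concern holds. Section 9.3.4 conflicts with Section 9.3.1, and any reading on which it is not redundant removes valid PK data. For one active MAD subject withdrawn after the Day 1 profile, 16 or 19 of 40 plasma samples go unused, and Day 1 precision falls by 18% without replacement or 13% with it. These ratios assume log-normality but no particular CV.

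The result is conditional on a dropout occurring and on the sentence being applied as written. Bias would follow only if leaving is related to exposure, which the document does not establish. If dropout were taken to mean not completed under Section 7.1, a subject missing only the follow-up visit would lose all 40 samples; Section 4.1 points the other way, so this shows the ambiguity and is not the expected loss. No effect is claimed on the any-subject PK stopping limits. The sentence should be corrected, but it does not threaten the primary objective.

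**What to change.** Delete the sentence from Section 9.3.4 and let the Section 9.3.1 PK set govern. State that the non-compartmental analysis uses each evaluable profile, such as Day 1 for a subject who leaves later, and that the NONMEM model uses all valid concentrations up to withdrawal. Flag parameters that cannot be estimated, and list every PK exclusion with its reason. If the sentence is kept, define *dropout* so that Sections 9.3.1 and 9.3.4 agree, and say whether it covers a subject off treatment but still followed and one who misses only the follow-up visit.

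The cost is protocol and SAP wording, with no extra samples or visits. PK tables would show different n across parameters and days.
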